**Table 4. Criteria to Potentially Clinically Significant (PCS) Laboratory Abnormalities**

Clinical Laboratory Outlier Criteria		
Parameter name	PCS Low	PCS High
HEMATOLOGY		
White blood cells	$< 3.0 \times 10^9/\text{L}$	$> 16 \times 10^9/\text{L}$
Neutrophils	$< 1.5 \times 10^9/\text{L}$	$> 13.5 \times 10^9/\text{L}$
Red blood cells	$\leq 3.5 \times 10^{12}/\text{L}$	$\geq 6.4 \times 10^{12}/\text{L}$
Hemoglobin - Females	$\leq 95 \text{ g/L}$	$\geq 175 \text{ g/L}$
Hemoglobin - Males	$\leq 115 \text{ g/L}$	$\geq 190 \text{ g/L}$
Hematocrit - Females	$\leq 32\%$	$\geq 54\%$
Hematocrit - Males	$\leq 37\%$	$\geq 60\%$
Platelet count	$\leq 75 \times 10^9/\text{L}$	$\geq 700 \times 10^9/\text{L}$
BLOOD CHEMISTRY		
Alanine aminotransferase (ALT)	N/A	$> 3 \times \text{ULN}$
Aspartate aminotransferase (AST)	N/A	$> 3 \times \text{ULN}$
Alkaline phosphatase (ALP)	N/A	$> 3 \times \text{ULN}$
Total bilirubin	N/A	$> 1.5 \times \text{ULN}$
Blood urea nitrogen (BUN)	N/A	$\geq 10.7 \text{ mmol/L}$
Creatinine	N/A	$\geq 176.8 \mu\text{mol/L}$
Sodium	$\leq 126 \text{ mmol/L}$	$\geq 156 \text{ mmol/L}$
Potassium	$\leq 3 \text{ mmol/L}$	$\geq 6 \text{ mmol/L}$
Bicarbonate	$\leq 16 \text{ mmol/L}$	$\geq 35 \text{ mmol/L}$
Glucose	$\leq 2.2 \text{ mmol/L}$	$\geq 9.7 \text{ mmol/L}$

Clinical Laboratory Outlier Criteria		
Parameter name	PCS Low	PCS High
Calcium	$\leq 2$ mmol/L	$\geq 3$ mmol/L
Phosphorus	$\leq 0.6$ mmol/L	$\geq 1.7$ mmol/L
Albumin	$\leq 25$ g/L	$\geq 625$ g/L
ULN = upper limit of normal		

### By-visit Summaries

- For numerical laboratory parameters, actual values, change from baseline and percent change from baseline will be summarized by visit.
- Number of evaluable participants, mean, standard deviation, quartiles, min and max values will be presented at each visit.
- Plots of mean values (with standard error) for numeric laboratory parameters at each visit will be provided.
- Listings of individual laboratory measurements for all the parameters will be provided.

### Analysis of Blood Glucose

The blood glucose from local laboratory are collected at screening, Hours 0-12, Hour 24, Hour 48, Hour 72, Hour 96 and Day 7 with the normal ranges. Additionally, the Point-of-Care (POC) blood glucose is collected pre-dose, hourly up to Hour 96 without normal ranges. The normal range for POC blood glucose data are assigned as between 70 mg/dL and 139 mg/dL, according to the reference range recommended by the American Diabetes Association for random blood glucose measurements. For all analyses, the two sources of data (local laboratory and POC) will be combined and analyzed together.

Summary of lowest post-baseline value of blood glucose will be provided. The number (%) of participants with post-baseline blood glucose abnormalities ( $<55$  mg/dL,  $<80$  mg/dL,  $<120$  mg/dL) will be summarized by actual treatment group. Blood glucose values for participants with post-baseline blood glucose  $<55$  mg/dL will be listed.

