4.3.3. Benefit/Risk

BIIB093 has been shown to potentially reduce mortality associated with LHI, reducing brain edema, and improving functional outcomes.

BIIB093 given intravenously in a 3-stage dosing regimen over 72 hours was generally well tolerated in the population of participants with LHI and TBI. The only adverse drug reaction identified was hypoglycemia, which can be mitigated by frequent blood glucose (BG) measurement and dose adjustment. The safety profile of BIIB093 observed in completed studies in participant with LHI and TBI is detailed in the Investigator's Brochure. Based on the safety profile and observed benefit in Phase 2 studies of BIIB093 for treatment of LHI and TBI, Biogen

CONFIDENTIAL

The information contained herein may not be used, disclosed, or published without the written consent of
Biogen MA Inc.

considers that the benefit/risk profile of BIIB093 remains positive and supports the continued development of BIIB093 for the treatment of patients with LHI and brain contusion.

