11.4. Concomitant Therapy and Procedures

11.4.1. Concomitant Therapy

A concomitant therapy is any medication administered between enrollment through Day 180 or early discontinuation (whichever is earlier). All concomitant therapy, including but not limited to

CONFIDENTIAL

The information contained herein may not be used, disclosed, or published without the written consent of Biogen MA Inc.

dextrose solutions, osmotherapy, paralytics, sedatives, and vasoactive drugs will be recorded in appropriate eCRF.

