It is recommended that maintenance dextrose-containing IV solution be initiated when BG is < 120 mg/dL (~6.7 mmol/L) and maintained for the duration of the study treatment administration (up to 96 hours) with the new glycemic BG target in the range of 140 to < 180 mg/dL (~7.8-10 mmol/L).

Table 5: Blood Glucose Monitoring and Management

Inpatient BG Level	BG Monitoring and Management ¹
Initiation of dextrose-containing IV solution	
< 120 mg/dL (~6.7 mmol/L)	
 It is recommended that D10NS at 35 to 50 mL/h be initiated as first-line management. Consider D5NS at a rate of 70 to 100 mL/h or other percent dextrose solutions as alternatives.
Maintenance of dextrose-containing IV solution after initiation	
≥ 180 mg/dL (~10 mmol/L)	
 It is recommended that dextrose-containing IV solution be titrated downward or stopped temporarily until BG is ≥ 140 to < 180 mg/dL (~7.8 to ~10 mmol/L).
< 180 mg/dL (~10 mmol/L) but ≥ 140 mg/dL (~7.8 mmol/L)	
 It is recommended that dextrose-containing IV solution be maintained or titrated to keep BG as ≥ 140 mg/dL (~7.8 mmol/L) but < 180 mg/dL (~10 mmol/L).
< 140 mg/dL (~7.8 mmol/L) but ≥ 80 mg/dL (~4.4 mmol/L)	
 Insulin and other BG-lowering agents are not permitted during study treatment administration when BG is < 140 mg/dL (~7.8 mmol/L). It is recommended that dextrose- containing IV solution be maintained when BG is < 140 mg/dL (~7.8 mmol/L). Titrate up the IV infusion rate to keep BG ≥ 140 mg/dL (~7.8 mmol/L) but < 180 mg/dL (~10 mmol/L)
< 80 mg/dL (~4.4 mmol/L)	
 It is recommended that the infusion rate of the dextrose-containing IV solution be increased to keep BG ≥ 140 mg/dL (~7.8 mmol/L) but < 180 mg/dL (~10 mmol/L).
< 70 mg/dL (~3.9 mmol/L)	
 Test must be repeated to confirm level. Must be treated with 50 mL of dextrose 50% in water or equivalent. It is recommended that the infusion rate of the dextrose-containing IV solution be increased after the dextrose bolus.

CONFIDENTIAL

The information contained herein may not be used, disclosed, or published without the written consent of Biogen MA Inc.

Inpatient BG Level	BG Monitoring and Management ¹

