#### 5.5.2. Concomitant Medications

All concomitant medications will be coded using the World Health Organization (WHO) medication dictionary.

- Number (%) of participants taking any concomitant medications will be summarized by randomized treatment group and total and by indication for mITT participants.
- A listing of concomitant medications for randomized participants will be presented.

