#### **Shift Analyses**

Laboratory abnormalities will be summarized with shift tables. Tables will present changes relative to each parameter's normal ranges. Each participant's hematology and blood chemistry values will be flagged as "low", "normal", or "high" relative to the normal ranges of the local laboratory or as "unknown" if no result is available.

Shifts from baseline to high/low status for hematology and blood chemistry parameters will be presented. In each summary, the denominator for the percentage is the number of participants at risk for the shift. The number at risk for shift to low is the number of participants whose baseline value was not low and who had at least one post-baseline value. The number at risk for shift to high is the number of participants whose baseline value was not high and who had at least one post-baseline value. Participants will be counted only once for each parameter and each type of shift regardless of how many post-dosing assessments had that type of shift. Participants with shift to low or high will be listed by laboratory parameter and shift type.

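### The readable SAP plans no safety-set summary, by actual treatment group, of the dextrose given to hold glucose up, so blood glucose and AESI results may understate the drug's glucose-lowering effect

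*SAP*

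**What the plan says.** **Known harm.** Protocol 4.3.3 states: "The only adverse drug reaction identified was hypoglycemia". Protocol 4.5.1.2 adds that severe hypoglycemia was seen at 6 and 10 mg/day but not at 3 mg/day, that no dose between 3 and 6 mg/day had been evaluated clinically, and that exposure at 5 mg/day is simulated.

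**Glucose management.** Protocol 11.4.1.1.1: "It is recommended that maintenance dextrose-containing IV solution be initiated when BG is < 120 mg/dL", with a target of 140 to < 180 mg/dL. Table 5 recommends raising the dextrose rate at < 80. At < 70, after a confirmatory test, it says: "Must be treated with 50 mL of dextrose 50% in water or equivalent". At < 55 the study-drug rate must be reduced.

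**Recording.** Protocol 11.4.1: "dextrose solutions, osmotherapy, paralytics, sedatives, and vasoactive drugs will be recorded in appropriate eCRF". Protocol 14.1 repeats this under clinical safety assessments.

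**Glucose analyses.** SAP 5.7.4: "Summary of lowest post-baseline value of blood glucose will be provided", plus number (%) below 55, 80 and 120 mg/dL by actual treatment group and a listing of participants below 55. Point-of-care (POC) and laboratory values are combined. For shift tables, "The normal range for POC blood glucose data are assigned as between 70 mg/dL and 139 mg/dL" and "Shifts from baseline to high/low status for hematology and blood chemistry parameters will be presented".

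**Other hypoglycemia outputs.** These are the AESI tables and hypoglycemia listings (SAP 5.7.2), the AE and SAE tables including AEs leading to interruption, rate change or dose reduction (SAP 5.7.1), and rate changes with reasons (SAP 5.5.1).

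**Dextrose.** The only table that would contain it is in SAP 5.5.2: "Number (%) of participants taking any concomitant medications will be summarized by randomized treatment group and total and by indication for mITT participants". A listing covers randomized participants.

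**The concern.** When a variable is steered toward a target, its observed values show what is left after treatment. If the drug pushes glucose down and staff respond with dextrose, part of the drug effect moves out of the BG record and into the dextrose record. An analysis that reports the first without the second can make arms look more alike than they are.

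Two questions depend on this. One is how far the drug lowers glucose relative to placebo. The other is how much more glucose support 5 mg/day needs than 3 mg/day, which matters when choosing a dose in a range that had not been tested clinically.

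The one table that would count dextrose is also poorly placed to answer. It uses the mITT set, so it leaves out dosed participants without a qualifying centrally read scan. It groups by randomized rather than actual treatment. It promises no dextrose row, amount or bolus count.

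**Working it through.** The plan states no rate, precision or power for hypoglycemia or dextrose use, so there is no figure to reproduce. The check traces each planned output against the protocol's glucose levels, and then illustrates the attenuation.

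**1. What each output captures**

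| Planned output | Relation to dextrose |
|---|---|
| BG < 120 count | At the level for starting dextrose, so largely ahead of it. But 120 lies inside the SAP's assigned POC normal range (70 to 139), so the count mixes normal readings with drug effect. |
| BG < 80 count | At the level for increasing dextrose. Maintenance dextrose already running can prevent the reading. |
| Shift to low (POC limit 70) | Close to a < 70 count for POC readings; laboratory values use local ranges. A bolus cannot erase the reading that triggered it. Earlier maintenance dextrose can prevent that reading. |
| BG < 55 count, AESI | Below the levels for both maintenance dextrose and bolus. |
| AE tables | A result needing corrective therapy meets an AE criterion (Protocol 15.1.1), but the Investigator decides. Preventive dextrose need not produce an AE. |
| Rate changes | Glucose-driven reductions are tied to < 55 (Protocol 11.2), so they inherit that filter. |
| Potentially clinically significant (PCS) glucose | The low limit of 2.2 mmol/L is 2.2 × 18.016 = 39.6 mg/dL, well under 55. The high limit of 9.7 mmol/L is 9.7 × 18.016 = 174.8 mg/dL, inside the dextrose target range. |

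None reports how many participants were started on dextrose, how many boluses they had, or how much dextrose they received.

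**2. Size of the blunting (all rates assumed)**

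Let p_A and p_P be the proportions on drug and placebo who would cross a BG cut-off below 120 mg/dL without preventive dextrose, and let f be the share averted. With the same f in both arms:

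observed difference = (1 − f) × (p_A − p_P)

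| Without dextrose | f = 0 | f = 0.5 | f = 0.8 |
|---|---|---|---|
| 10% vs 2% | 8 points | 4 | 1.6 |
| 20% vs 5% | 15 points | 7.5 | 3 |
| 30% vs 5% | 25 points | 12.5 | 5 |

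If drug-arm participants receive more dextrose, f is larger there and the difference shrinks further. With 20% vs 5%, f = 0.8 on drug and 0.5 on placebo: 0.2 × 20 − 0.5 × 5 = 4 − 2.5 = 1.5 points.

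**3. What a dextrose table could show**

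For one dose (40) against pooled placebo (80), the 95% half-width is 1.96 × √[p_A(1 − p_A)/40 + p_P(1 − p_P)/80].

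- 50% vs 20%: 1.96 × √(0.00625 + 0.00200) = 17.8 points.
- 60% vs 40%: 1.96 × √(0.00600 + 0.00300) = 18.6 points.
- 5 vs 3 mg/day (40 vs 40) at 60% vs 50%: 1.96 × √(0.00600 + 0.00625) = 21.7 points.

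Such tables would be descriptive. They could show a large difference in glucose support, not a fine one.

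**The case against.** The strongest reply is that the SAP already sees most of the lows that matter. The lowest-value summary uses all post-baseline readings, including the one that triggers a bolus, so a protocol-triggered bolus cannot hide its participant. The < 80 count includes everyone below 70. The shift-to-low table, with a POC limit of 70, comes close to the bolus trigger. Nearly everyone is at risk for that shift, because exclusion criterion 21 cites screening BG < 70. AE, AESI and rate-change tables use actual treatment group. This stands. A reader might infer that hypoglycemia is judged only from BG values measured after dextrose; the documents do not support that. Nor do they support gauging the gap by setting bolus use against the < 55 table alone, since the < 80 and shift tables would register those same participants.

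Three further replies carry weight.

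- Starting dextrose is recommended and subject to medical judgment, so use will also reflect site practice and nutrition.
- The documents say that dextrose is recorded, but do not show that concentration, volume, rate or a bolus flag is captured. Total grams may not be derivable.
- Protocol 16.3 and 16.4 and SAP 5.8 and 5.9 are blacked out. Protocol 4.5.1.2 treats blood glucose as pharmacodynamic data, and Protocol 16 promises exposure-response analyses for safety. A related output may sit in redacted text.

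These replies narrow the point without removing it. Readings prevented by maintenance dextrose leave no trace in any BG cut-off below 120 mg/dL, and no readable output shows the amount of support given.

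**Conclusion.** The point holds as a reporting gap. Dextrose is the protocol's main means of holding glucose up against the drug's only identified adverse reaction, and it is recorded as a safety item. Yet the readable SAP plans no safety-set summary of it by actual treatment group. BG and AESI results may therefore understate the glucose-lowering difference between drug and placebo and between doses, and the amount of glucose support each dose needed would not be reported.

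A reader might go further and conclude that the harm is understated. The documents do not support that: they give no hypoglycemia or dextrose rates, so neither the presence nor the size of an understatement can be established. The attenuation figures rest wholly on assumed rates and an assumed share averted. The direction rests on two assumptions: that dextrose use follows the recommendation closely enough to prevent some low readings, and that drug-arm participants need it at least as often as placebo participants. The conclusion also assumes that the redacted sections hold no such summary.

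The planned safety analysis is not invalid. This is a worthwhile, low-cost addition to it.

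**What to change.** In SAP 5.7.4, for the safety analysis set by actual treatment group (placebo, 3 mg/day, 5 mg/day, combined), add:

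- number (%) started on maintenance dextrose;
- number (%) with any rescue dextrose bolus, and boluses per participant;
- total dextrose from Hour 0 to Hour 96, where the recorded fields allow it to be derived;
- number (%) with BG < 70 mg/dL, beside the existing < 55, < 80 and < 120 counts.

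Before finalising, check which dextrose fields the eCRF holds, and drop or simplify the total if they are insufficient. If a redacted section already plans these outputs, a cross-reference from 5.7.4 is enough.

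The cost is SAP wording, minor programming and one or two tables, with no new data collection intended. The downside is a hypoglycemia picture that may look less favourable. Nothing here changes, or suggests changing, how glucose or study drug is managed.

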### Analysis of Liver Function Tests

Potential serious hepatotoxicity is defined as alanine aminotransferase (ALT) or aspartate aminotransferase (AST)  $\geq 3 \times$  upper limit of normal (ULN) and total bilirubin  $> 2 \times$  ULN at any time post-baseline, not necessarily concurrent (i.e., on the same day).

A scatterplot of the maximum post-baseline ALT or AST value relative to ULN and maximum post-baseline total bilirubin value relative to ULN (not necessarily concurrent) for each

participant will be provided. A line plot of ALT, AST, alkaline phosphatase (ALP) and total bilirubin values over time for participants with potential serious hepatotoxicity will be provided.

In addition, the number (%) of participants meeting the laboratory abnormality criteria listed below will be summarized, respectively:

- ALT > 3 × ULN
- ALT > 5 × ULN
- AST > 3 × ULN
- AST > 5 × ULN
- AST or ALT > 3 × ULN
- AST or ALT > 5 × ULN
- Total Bilirubin > 2 × ULN
- ALP > 1.5 × ULN
- AST or ALT > 3 × ULN and Total Bilirubin > 2 × ULN

Concurrent is defined as on the same day. A listing of participants with potential serious hepatotoxicity will be provided.

#### **5.7.5 Electrocardiogram (ECG)**

The number (%) of participants with shifts to categorical values (abnormal not AE, or abnormal AE) will be summarized by actual treatment group. ECG parameters include heart rate, PR Interval, RR Interval, QRS Duration, QT Interval, QTcF, and QTcB, where QTcB is calculated as QT/(RR/1000)1/2. The actual values and change from baseline for each of the ECG parameters will be summarized by actual treatment group and by visit summary. If there are multiple records fall into the same visit windows, the worst record will be presented in the summary.

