8.2. Exclusion Criteria

Candidates will be excluded from study entry if any of the following exclusion criteria exist at Screening, or at the timepoint specified in the individual criterion listed:

1. In the judgment of the Investigator, patient is likely to have supportive care withdrawn within 24 hours.
2. Indication for immediate evacuation of IPH or DC.
3. Clinical signs of brainstem herniation, in the opinion of the Investigator.
4. NCCT or MRI evidence of penetrating brain injury impacting the brain parenchyma. Cerebrospinal fluid leak in isolation is not exclusionary unless evidence of parenchymal penetration by an external force (e.g., blunt object, bullet, or depressed skull fracture).
5. Any presence of midbrain or posterior fossa injury as assessed by imaging and clinical examination.
6. Symptoms and imaging suggestive of diffuse axonal injury as the predominant injury, in the opinion of the Investigator.
7. Intracranial hemorrhage due to causes other than TBI (e.g., spontaneous intracerebral hemorrhage, saccular/fusiform/infective aneurysm rupture), based on medical history of no trauma and location of the bleed.

CONFIDENTIAL

The information contained herein may not be used, disclosed, or published without the written consent of Biogen MA Inc.

8. Coagulopathy (international normalized ratio [INR] > 1.5, activated partial thromboplastin time [PTT] > 60 s, or fibrinogen < 1.0 g/L), severe anemia (hemoglobin < 85 g/L), or thrombocytopenia (platelets < 75,000 cells/mm³) at Screening.
9. Symptoms, in the opinion of the Investigator, or electrocardiogram (ECG)-based signs (QT interval corrected for heart rate [QTc] > 520 ms) of myocardial ischemia or unstable angina at Screening, based on local assessment.
10. ECG evidence of second- or third-degree heart block or cardiac arrhythmia associated with hemodynamic instability.
11. Presence of concomitant spinal cord injury as assessed by imaging and clinical examination.
12. Injury to ascending aorta, carotid, or vertebral arteries.
13. Severe or unstable concomitant condition or disease (e.g., known significant neurologic deficit, cancer, sepsis, hematologic or coronary disease) that in the opinion of the Investigator may increase the risk of study participation or uninterpretable results, if known.
14. Patients with, in the opinion of the Investigator, life expectancy < 3 months not related to current brain contusion, or those unlikely to be compliant with follow-up.

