10. DISCONTINUATION OF STUDY TREATMENT AND WITHDRAWAL OF PARTICIPANTS FROM THE STUDY

10.1. Discontinuation of Study Treatment

A participant *must* permanently discontinue study treatment for any of the following reasons:

- If hypoglycemia cannot be rectified by the treating team, the severity and length of hypoglycemia is determined by the Investigator to be harmful to the participant, and the infusion rate has already been reduced to 0.0795 mg/h (refer to the Directions for Handling and Administration [DHA] for corresponding mL/h rate) for > 30 minutes.
- QT/QTc (formula not specified) of > 550 ms from local assessment, if the measurement is obtained and confirmed with a second ECG reading within 15 minutes.
- Confirmed alanine aminotransferase (ALT) or aspartate aminotransferase (AST) > 5 × upper limit of normal (ULN) or confirmed ALT or AST > 3 × ULN and bilirubin > 2 × ULN.
- The participant has a positive pregnancy test during the 96-hour time window of treatment.
- The participant experiences an AE that necessitates permanent discontinuation of study treatment.
- The participant experiences a medical emergency that necessitates unblinding of the participant's treatment assignment.
- The participant experiences a hypersensitivity or suspected allergic reaction to study treatment, based on the Investigator's assessment.
- Informed consent withdrawal.
- At the discretion of the Investigator for medical reasons.

If the study treatment infusion is stopped as a result of low BG, please refer to the guidance in Section 11.4.1.1.1, Table 5. Investigators must also use their own medical judgment in conjunction with referencing the guidance. The primary reason for discontinuation of study treatment must be recorded in the participant's electronic case report form (eCRF). All participants who discontinue treatment, except for those who withdraw consent, will be followed to the end of study.

If a site learns, while a participant is receiving study treatment, that the participant had taken sulfonylureas within 24 hours prior to or during the hospital stay, this will not be a cause for discontinuation of study treatment or of withdrawal from the study.

CONFIDENTIAL

The information contained herein may not be used, disclosed, or published without the written consent of Biogen MA Inc.

Participants who discontinue treatment should be encouraged to remain in the study and continue protocol-required tests and assessments.

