16.2.2. Methods of Analysis

16.2.2.1. General Considerations

Summary statistics will be presented by treatment group. By-treatment-group analysis will be displayed as placebo, BIIB093 3 mg/day, BIIB093 5 mg/day, BIIB093 combined, and total (if applicable). For continuous endpoints, summary statistics will generally include the number of participants with data, mean, SD, median, quartiles, and range. For categorical endpoints, frequency and percentage of participants in each category will be presented. Statistical testing for efficacy endpoints will be performed between the BIIB093 (3 mg/day or 5 mg/day) and placebo groups. All tests will be 2-sided with a significance level equal to 0.05 (unless otherwise specified).

CONFIDENTIAL

The information contained herein may not be used, disclosed, or published without the written consent of Biogen MA Inc.

Multiplicity will not be adjusted for the tests of the primary and secondary endpoints.

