16.6.2.3. ECG

The number and percentage of participants with shifts to categorical values (abnormal but not an AE, or abnormal AE) will be summarized by treatment group.

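### SAP 5.7.5 counts no participants with marked QTc prolongation and plans no ECG listing, although a confirmed QT/QTc above 550 ms is a mandatory stop

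*SAP*

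**What the plan says.** SAP 5.7.5 describes two ECG outputs.

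- A categorical one: "The number (%) of participants with shifts to categorical values (abnormal not AE, or abnormal AE) will be summarized by actual treatment group". Protocol 16.6.2.3 plans the same analysis and no other for ECG.
- A continuous one. The variables are listed as "ECG parameters include heart rate, PR Interval, RR Interval, QRS Duration, QT Interval, QTcF, and QTcB", and then: "The actual values and change from baseline for each of the ECG parameters will be summarized by actual treatment group and by visit summary". No statistics are named. For repeat tracings the rule is: "If there are multiple records fall into the same visit windows, the worst record will be presented in the summary".

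The protocol uses a QTc figure in two places. Section 10.1 makes permanent discontinuation mandatory for "QT/QTc (formula not specified) of > 550 ms from local assessment", provided a second ECG confirms it within 15 minutes. Exclusion criterion 9 in Section 8.2 bars patients with symptoms or ECG-based signs ("QT interval corrected for heart rate [QTc] > 520 ms) of myocardial ischemia or unstable angina at Screening"), on local assessment. Protocol Table 3 schedules six ECGs after the infusion starts, at Minute 5 and at Hours 6, 24, 48, 72 and 96.

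**The concern.** The gap shows when the SAP's safety outputs are set against the protocol's stopping criteria. Section 10.1 names three measurements that can force a stop: hypoglycemia, QT/QTc, and ALT/AST with or without bilirubin. For two of them the SAP counts participants beyond limits and lists cases. For QTc it does neither. Vital signs have no stopping limit, yet they get counts and a listing.

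At stake is a plain descriptive question: how many participants on 3 mg/day, on 5 mg/day and on placebo had marked QTc prolongation? Protocol 4.5.1.2 says that doses between 3 and 6 mg/day have not been evaluated clinically, so the ECGs at 5 mg/day are new information. ECG is also part of the interim safety package (SAP 4.1), and Protocol 16.7 allows that interim to lead to accelerated Phase 3 preparation.

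**Working it through.** **1. Outputs for the stopping measures, side by side.**

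| Measure | Protocol 10.1 | Counts beyond limits in the SAP | Listing in the SAP |
|---|---|---|---|
| Glucose | Unrectified hypoglycemia (defined elsewhere as < 55 mg/dL) | Yes: < 55, < 80, < 120 mg/dL (5.7.4) | Yes, for < 55 mg/dL |
| Liver tests | ALT/AST > 5 × ULN, or > 3 × ULN with bilirubin > 2 × ULN | Yes, including both of these criteria (5.7.4) | Yes, potential serious hepatotoxicity |
| QT/QTc | > 550 ms, confirmed | None (5.7.5) | None |
| Vital signs | No limit | Yes, Protocol Table 6 (5.7.6) | Yes |

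**2. Where an on-treatment QTc event would surface.**

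| Event | Planned output | Counted by dose? |
|---|---|---|
| Confirmed > 550 ms, infusion stopped | Discontinuation reasons (SAP 5.2); AE tables if recorded as an AE (5.7.1) | Yes, if recorded as the reason |
| > 550 ms, not confirmed | Abnormal shift at most; a maximum if a range is printed | No |
| Above 520 and up to 550 ms | Same | No |
| Large rise ending at or below 520 ms | Same, if the ECG is called abnormal at all | No |

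The AE tables do not fill the lower three rows reliably. Under Protocol 15.1.1 an abnormal ECG is an AE only if it meets SAE criteria, needs corrective therapy or is judged clinically significant. The Hour 96 ECG also falls at the planned end of infusion, so a prolongation first seen there may leave nothing to discontinue.

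**3. The plan's own figure.** The documents give no QTc figure. Their one design calculation concerns contusion volume (SAP 2.3) and serves here only to confirm group sizes. With 80 per group, a difference of 15 mL and an SD of 29 mL, 15 / (29 × √(2/80)) = 3.27 and Φ(3.27 − 1.96) = 0.905 (0.902 with the t distribution). The stated power of about 90% reproduces, with 40 per active dose and 80 on pooled placebo.

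**4. What a group mean would show.** The number prolonged, the size of the rise and the SD of change are all assumptions.

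- Shift in the dose-group mean = k × d / n, for k of n participants each rising by d ms. For k = 2, d = 80, n = 40: 2 × 80 / 40 = 4 ms. For k = 1 to 3: 1.5 to 4.5 ms at d = 60, and 2.5 to 7.5 ms at d = 100.
- SE of one dose against placebo = SD × √(1/40 + 1/80) = SD × 0.194. For SD 20, 30 and 40 ms: 3.87, 5.81 and 7.75 ms.
- 95% half-width = 1.96 × SE = 7.6, 11.4 and 15.2 ms.

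Every shift in this range lies within the half-width, though the largest (7.5 ms) only just does at SD 20. Median and quartiles would barely move with 1 to 3 of 40 affected. A maximum would show the largest value at a visit, but not how many participants crossed a cut-off over six ECGs.

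**5. What a count would show.** Exact 95% intervals for 40 participants: 1/40 = 2.5% (0.1 to 13.2); 2/40 = 5.0% (0.6 to 16.9); 3/40 = 7.5% (1.6 to 20.4); 0/40 has an upper limit of 8.8%. If the true rate were 2% or 5% (assumed), the chance of at least one case among 40 is 1 − 0.98^40 = 55% or 1 − 0.95^40 = 87%.

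**The case against.** A reader might infer that the SAP reports only means and so averages QTc outliers away. The text does not say that. Section 5.7.5 names no statistics. Where the documents do name them, the range is usually included: Protocol 16.2.2.1 says that "summary statistics will generally include the number of participants with data, mean, SD, median, quartiles, and range", and SAP 5.7.4 gives minimum and maximum for laboratory values. Neither passage is written for ECG, but a printed maximum is plausible, and taking the worst record in a window favours extremes.

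Nor would a breach of the stopping limit vanish. A confirmed reading above 550 ms forces a stop whose primary reason goes into the eCRF. SAP 5.2 summarizes and lists those reasons, and SAP 5.7.1 tabulates and lists AEs leading to early termination of infusion.

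Three further points stand.

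- The 520 ms figure is an entry criterion, worded as a sign of ischemia or unstable angina. It is not an on-treatment limit.
- A participant with an abnormal ECG at baseline could still move to the abnormal-and-AE category, so the shift analysis may miss a QTc rise but is not bound to.
- The protocol describes no QT signal; Section 4.3.3 names hypoglycemia as the only adverse drug reaction identified. The SAP plans no ECG test, so the standard errors above only show how little a mean reveals.

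Finally, part of the SAP 5.7 heading and all of 5.8 and 5.9 are redacted. Related ECG content there cannot be excluded, although 5.7.5 itself reads as intact.

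These points narrow the concern without removing it. None of the visible outputs counts unconfirmed readings, values between the two figures, or large rises.

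**Conclusion.** The concern holds as a reporting gap of low severity. SAP 5.7.5 has no participant count by QTc value or by size of increase, and no ECG listing, in contrast to its treatment of glucose, liver tests and vital signs. What is lost is the number per dose with marked prolongation short of a confirmed, recorded stop. The absence is read directly from the text and rests on no numerical assumption. The illustration of a 4 ms shift against an SE of 3.9 to 5.8 ms depends wholly on assumed values and is no estimate of any effect of the drug. The documents do not support concluding that BIIB093 prolongs QTc, that confirmed stops would go unreported, or that either clinical limit is wrong.

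**What to change.** In SAP 5.7.5, before the Day 4 administrative database lock, add the following for the safety analysis set by actual treatment group.

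1. The number (%) of participants whose maximum post-baseline QTcF exceeds 520 ms and 550 ms, among those not above that cut-off at baseline. These are the protocol's own figures, used only as reporting cut-offs.
2. The number (%) whose QTcF increase from baseline exceeds sizes that the sponsor pre-specifies.
3. A listing of participants above 550 ms, showing whether the reading was confirmed and whether it led to discontinuation.
4. A note that the table uses QTcF, whereas the stopping rule rests on local assessment with the correction formula unspecified. The table therefore need not match the stops one for one; the listing links the two.

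The cost is one table, one listing and a few lines of SAP text, using ECGs already collected. No clinical rule changes. With about 40 participants per dose the counts will be small and support description only.
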